Breast cancer is the most frequently diagnosed cancer in women in developed countries. An estimated 226,000 new cases of invasive breast cancer and 39,920 deaths are expected to occur in 2012 in the United States [1]. Although the average lifetime risk of breast cancer in an American woman is one in eight, the risk is increased in women with a strong family history of breast cancer, BRCA 1 and 2 gene mutations, atypical hyperplasia or lobular carcinoma in situ (LCIS), and history of mantle irradiation for Hodgkin's disease[2]. Although new systemic treatments for established breast cancer has shown to reduce mortality[3], but the success rate is low. Major breakthroughs have come slowly, and greater attention is now being directed towards breast cancer prevention[4]. One particularly promising strategy has been to use medication to prevent breast cancer development.

Selective estrogen receptor modulators (SERMs)/Aromatase Inhibitors: The SERM, tamoxifen has been used in the treatment of breast cancer for many years. The observation that contralateral breast cancer was reduced in women treated with tamoxifen led to a number of chemoprevention trials with tamoxifen and eventually raloxifene. Results from such breast cancer prevention trials summarized in an overview analysis showed that SERMs significantly reduced breast cancer incidence by 38%[5]. Exemestane, an aromatase inhibitor evaluated in a double-blind, placebo controlled phase III study in 4560 postmenopausal women, demonstrated a 65% relative reduction in the annual incidence of invasive breast cancer as well as 53% decrease in the annual incidence of invasive plus noninvasive breast cancer[6]. Studies using selective estrogen receptor modulators, or SERMs, have shown that breast cancer prevention is feasible[5]. However, while breast cancer incidence is reduced by approximately 50% in these studies, not all cancers are prevented. First, there is no reduction of estrogen receptor (ER)-negative tumors. Secondly, even ER-positive tumors are only reduced by one-half to two-thirds. Because SERMs do not totally prevent breast cancer and because of the side effects of long-term SERM use, the majority of risk-eligible women are reluctant to take chronic antiestrogen therapy for primary prevention. Chronic therapy is necessary because these drugs suppress proliferation, but do not remove abnormal, premalignant cells. Thus, there is an urgent need to develop more effective strategies to prevent breast cancer that are tolerable to women at risk. Several nutritional studies have shown inverse relationship between the consumption of olive oil and the incidence of breast cancer[7]. Many of the beneficial properties of olive oil are associated with minor components of which hydroxytyrosol (HT) is the most promising.

The primary reasons for targeting pre and post-menopausal high-risk women are 1) epidemiological studies have suggested an association between increase in olive oil intake and reduction in breast cancer risk 2) Studies have shown a correlation between decrease in mammographic density and decrease in breast cancer risk in both pre and post menopausal women 3) there is a need for a compound that prevents all types of breast cancer and has less toxicity

Imaging and tissue-based biomarkers have been incorporated into this trial and as new information becomes available during the course of this trial, this study will provide a useful biorepository to draw from for biomarker discovery in future studies.

The purpose of this trial is to evaluate the effect of hydroxytyrosol on mammographic density in women at high risk of breast cancer, and secondarily to gain information concerning the ability of hydroxytyrosol to modulate the expression of breast tissue markers and serum markers.

1.2 Introduction to the investigational Product(s)

[figure not shown]
Hydroxytyrosol is a product of hydrolysis of oleuropein and due to its polar character it is found in great quantities in the remains from oil processing such as pomace olive oil, olive-mill waste water, or the rinse waters[8]. Preclinical studies have demonstrated HT to have anti-atherogenic, cardioprotective, anti-inflammatory, platelet aggregation inhibitor, and antimicrobial properties. This natural compound has been reported to regulate transcription factors (Nrf2, NF κ B), cytokines (IL-6), prostaglandins (PGE2), COX-2, myeloperoxidase and response to stress through Wnt pathway[8-13]. Preclinical *in vivo* studies demonstrated the potent antioxidant HT to have an anti-neoplastic role by interacting with Wnt/sFRP signaling pathway.

Wnt/ β -catenin in Breast Cancer: Wnt/ β -catenin signaling pathway is an important regulator of the stem cell pathway controlling the development of the mammary gland during embryogenesis. This pathway is also frequently found in invasive breast cancer and leads to a more aggressive phenotype and poor clinical outcome through the regulation of important cell events like proliferation, migration, differentiation, and apoptosis[14]. The sFRP family consists of five secreted glycoproteins (sFRP1-5) that function as Wnt pathway inhibitor by directly interacting with both Wnt ligands and FRP receptors. sFRP family are silenced in several types of cancers including breast cancer[14, 15]. The Wnt/ β -catenin pathway has also been implicated in the control of stem cells[16]. Recently, it has been demonstrated that sFRP4 generate ROS (Reactive Oxygen Species)[17] by blocking Wnt/ β -catenin and resulting in oxidative stress. **Effects of Hydroxytyrosol on Wnt pathway:** The *in vivo* antitumor activity of HT was evaluated in an animal model of breast carcinogenesis[18], where the authors treated breast tumor-bearing rats with 0.5mg/kg HT for 5 days/week for 6weeks by oral gavage. They reported HT decreased tumor volumes in rat models to the same degree as treatment with adriamycin. HT also caused a marked decrease in tumor cell proliferation, and differential expression of genes related to apoptosis, cell proliferation, survival, and response to stress through inhibition of Wnt. Also a dose dependent decrease of β -catenin and cyclin D1 protein levels were observed. Similar findings were seen in epithelial to mesenchymal markers, a decrease in both Snail and Slug transcription factors and an increase in protein levels of epithelial marker E-Cadherin.

1.2.1 Preclinical Evidence for the Chemopreventive effects of HT

Antitumor *in vitro* studies have reported antiproliferative action due to overexpression of p21 and p27, and inhibition of CDK6, and pro-apoptotic events through activation of caspase-3. Moreover, regulation of NF κ B, COX-2, and PGE2 are also involved in regulation of carcinogenesis attributed to HT[8-13, 18]. An *in vitro* study assessing HT effects on human promyelocytic leukemia cells and colon adenocarcinoma demonstrated that HT arrested cell cycle and induced apoptosis in tumor cells by arresting the cells in G0/G1 phase[19]. An *in vitro* study in MCF-7 human breast cancer cells demonstrated a similar finding of cell cycle arrest in G0/G1 phase resulting in a dose dependent growth inhibition[10].

Figure 1-1 Chemical structure of Hydroxytyrosol

1.2.1.1 Epidemiological Evidence for the Chemopreventive effects of Olive oil

In comparison with Northern European or other Western countries, Mediterranean countries have lower rates of mortality from cardiovascular disease and cancer. This is partially attributed to the so-called Mediterranean diet. Historically, scientific efforts have been focused on healthful benefits of olive oil as key element of a Mediterranean diet. Numerous preclinical, animal studies and at least six case-control and one cohort study has been conducted to test the health benefits of olive oil. A meta-analysis evaluating relative risk (RR) estimates for high as opposed to low olive oil consumption that demonstrated reduction of the incidence of breast cancer by 38% (RR 0.62 95% CI 0.44-0.88). One of the limitations for the meta-analysis was different definitions of the high olive oil consumption which ranged from two teaspoons a day, more than once a day, consuming 40.7g/day, or more than 8.8g/day. Despite that, it supports an inverse association between olive oil consumption and breast cancer risk[7]. Traditionally, many of the healthful properties associated with this edible oil have been ascribed to its high content MUFA (monounsaturated fatty acids), such as oleic acid. Today, it is clear that many of the beneficial properties derived from the consumption of virgin olive oil are due to some of its minor compounds. The bulk of the research has focused on one of those compounds phenol hydroxytyrosol (HT).

1.2.1.2 Toxicology studies

Oral administration of a single gavage dose of solid olive-pulp extract at levels of 0, 1,000, 1,500 or 2,000 mg caused no adverse effects, except for soft or liquid feces. The rats were administered 5000mg/kg of olive pulp extract for 29 consecutive days and no mortality or clinical signs of toxicity were noted. The authors reported that the LD₅₀ of solid olive-pulp extract was greater than 5g/kg (equivalent to 2.5-3.5g/kg of HT) suggesting that the extract is non toxic[20].

1.2.1.3 Clinical Studies in HT

In a multicenter, randomized, crossover, controlled trial of 200 healthy male volunteers were randomized to olive oils with high (hydroxytyrosol content 63.5mg/L, tyrosol 24.4mg/L, and oleuropein derivatives 327.2mg/L), moderate(hydroxytyrosol content 28.5mg/L) and low (no hydroxytyrosol) [21]. There was a linear increase in high-density lipoprotein (HDL) cholesterol levels with increasing in phenolic (hydroxytyrosol) content with the mean change of 0.025, 0.032 and 0.045mmol/L respectively. Triglyceride levels decreased by an average of 0.05mmol/L for all three levels of olive oil. Oxidative stress markers also decreased with increasing phenolic content [21, 22]. Oxidative damage to lipids was assessed by measuring plasma-circulating oxidized LDL, plasma total F₂-isoprostanes, plasma C18 hydroxy fatty acids (GC-MS) and serum LDL cholesterol un-induced conjugated dienes. There was a

significant linear decrease in biomarkers of lipid peroxidation (conjugated dienes, hydroxyl fatty acids and oxidated LDL) with increasing phenolic content of olive oils. Based on these data, the European Food Safety Authority (EFSA) felt that a cause and effect relationship has been established and approved 5mg hydroxytyrosol and its derivatives in olive oil should be consumed daily [23].

Two studies have evaluated the absorption of HT in healthy volunteers. The first study administered pure HT as a supplement in an aqueous solution (single oral dose of 2.5 mg/kg) in the plasma and urine of 10 healthy volunteers[24]. They found that the absorption of HT is rapid, with maximal plasma concentration detected in 13 to 16 minutes and the levels were undetectable in 2 hours after administration. Another study administered 50ml olive oil in six healthy volunteers and demonstrated absorption of HT. The absorption was increased with sustained doses of olive oil [25]. An update in 2013 concluded a no observed adverse effects level (NOAEL) of 500mg/kg/day [26].

A dose of 25mg/day of HT was chosen due to following reasons 1) EFSA approved hydroxytyrosol as a healthy dietary compound up to 15mg/day. There is a previous unpublished study of using hydroxytyrosol 10mg BID in healthy volunteers with class I obesity (communication with PI). With this dose they did not see any changes in LDL oxidation levels and did not have any adverse effect. We used 25mg of hydroxytyrosol as there is demonstrated safety in previous studies and higher than usual healthy dietary compound.

2 Mammographic Density as a Marker of Breast Cancer Risk

Studies have consistently demonstrated a 4-6 fold increase in breast cancer risk for women with increased mammographic density for up to 8 years following measurement [25, 27, 28]. Breast density as assessed qualitatively by BI-RADS category (1= –almost entirely fat, 2 = –scattered fibroglandular densities, 3 = –heterogeneously dense, 4 = –extremely dense). Randomized studies have demonstrated that tamoxifen lowers mammographic breast density up to 4.3% yearly [29]. Given that tamoxifen has been shown to decrease the risk of breast cancer and does decrease breast density, density change may be a useful surrogate endpoint biomarker for the effect of tamoxifen and other chemopreventive agents on breast cancer incidence. A decrease in density of 1% could potentially translate into a nearly 2% lower risk of developing breast cancer [27]. **Effects of HT on Breast Density:** Data from epidemiological studies demonstrated that increase in olive oil intake was associated with decrease in breast densities[30]. A series of 2,000 women who had undergone routine regular mammography and who had detailed information regarding dietary and lifestyle available were evaluated. The authors reported that women in the highest tertile of olive oil consumption (>30.5 g/day) were associated with 30% reduction in breast density[30].

2.1 Methodology

The mammographic density will be classified by two different methods. Firstly, according to the American College of Radiology's Breast Imaging—Reporting and Data System (BIRADS), and secondly, by using the Cumulus software package developed by the Ontario Cancer Institute to assess percent density as a continuous measure (0-100% scale). The mammograms will be read for research purposes only. They will be read for clinical purposes at the time of the mammogram. The mammograms will be independently reviewed by two radiologists specializing in breast imaging. Quantitative classification of mammographic parenchyma will be based on radiological assessment after digitizing mammograms and measuring percentage density[28, 31].

2.2 Risk Assessment

- Breast Risk Calculation using the modified Gail risk score [32, 33]. This model is an interactive tool designed to estimate a woman's risk of developing invasive breast cancer in her lifetime and the next 5 years.
 - <http://www.cancer.gov/bcrisktool/>
 - This model can only be used if there is no known diagnosis of DCIS or LCIS
- A patient with a diagnosis of lobular carcinoma in situ (LCIS) or atypical lobular or atypical ductal hyperplasia. Germline mutations of BRCA 1 or BRCA 2 genes. Germline mutations in the PTEN (cowden syndrome) and TP53(Li-Fraumeni syndrome)
- History of unilateral breast cancer 5 years ago
- At least 10% probability of carrying BRCA mutation

3 Objectives and endpoints

Primary

- To conduct a pilot breast cancer prevention study of hydroxytyrosol in women at increased risk of breast cancer.
- To assess whether mammographic density is reduced in pre or post menopausal women at high risk of breast cancer taking hydroxytyrosol for 1 year compared with baseline.

Secondary

- To assess the toxicity of hydroxytyrosol
- To evaluate FACT ES score baseline, 6 months and 1 year.
-

Exploratory objectives (Mandatory biopsy)

[figure not shown]
- To assess whether proliferation (Ki67 staining, Cdkn2a tumor suppressor, cyclin D1), is reduced in women at high risk of breast cancer after taking hydroxytyrosol for 1 year compared with baseline.
- To explore the difference in the expression of other biomarkers of apoptosis (Fas receptor, cleaved caspase-3, caspase-8, cytochrome c), enzymes related to oxidative stress (Fas receptor, cleaved caspase-3, caspase-8, cytochrome c), DNA damage by immunohistochemistry, Wnt signaling(LRP6, β -catenin, Sfrp proteins 1 to 5, DKK1, c-jun, c-myc) and stem cell pathway before and after drug therapy.
- To collect and bank breast tissue from women at high risk of breast cancer prior to and after treatment with hydroxytyrosol for future biomarker analysis.

Exploratory endpoint (MRI Breast Imaging)

- To assess breast MRI density pretreatment and 12 months post hydroxytyrosol therapy in subjects with available breast MRIs.

4 Study design
4.1 Description of study design

A PILOT STUDY OF HYDROXYTYROSOL, A COMPONENT OF OLIVE OIL FOR BREAST CANCER PREVENTION IN WOMEN AT HIGH RISK OF BREAST CANCER

One hundred (100) pre and post-menopausal women at high risk of breast cancer who have declined tamoxifen, raloxifene or aromatase inhibitor (standard of care) will receive 25mg HT. Eligible women will have a 5 yr risk by Gail Model ≥ 1.7 , or 10% probability of BRCA mutation by BRCAPRO or similar model, or have a previous breast biopsy showing LCIS, atypical lobular or ductal hyperplasia, or have a known germline mutation in *BRCA1* or *BRCA2*. Patients with unilateral breast cancer 5 or more years prior to registration are also allowed. The main exclusion criteria include women who are pregnant or breast feeding, with diagnosis of any malignant disease, or with inability to take oral medication. The women will undergo a mammogram as well as a biopsy of normal breast tissue before and after taking study drug. This biopsy will be directed to the upper outer quadrant, which is typically a dense region. The primary endpoint of this study is change in mammographic density after treatment with HT. The Secondary endpoint will assess toxicity, apoptosis (Fas receptor, cleaved caspase-3, caspase-8, cytochrome c) and cell proliferation (Ki 67 staining, Cdkn2a tumor suppressor, cyclin D1), enzymes related to oxidative stress (ROS and related enzymes), DNA damage by immunohistochemistry, stem cell markers (CD44, CD24, and ALDH), and affection of Wnt signaling (LRP6, β -catenin, Sfrp proteins 1 to 5, DKK1, c-jun, c-myc) before and after drug therapy. If patients undergo a breast MRI before and/or after the completion of the drug, the images will be collected. The study drug will be supplied by PLThomas & Co.. The patients will have a study visit at 3, 6 and 12 months. The study visit will include a general history and physical exam, an assessment for safety and concomitant medications and pill

count. After completion of therapy, the patient will undergo a mammogram as well as a second breast biopsy.

5 Study Population

Each of the criteria in the following section must be met in order for a participant to be considered eligible for registration.

Study Duration:

The duration of patient participation in the study treatment will be a total of 12 months, which is counted from the start of treatment. Study Follow-up for all patients will include medical history update (30 days after the last dose of the study drug)

Safety Criteria:

All participants will be assessed by a physician for pre-existing medical conditions and baseline physical abnormalities prior to the initiation of investigational therapy. Patients presenting with any medical history, physical exam, or laboratory abnormality that, in the opinion of the treating physician, would put the subject's safety at risk will be excluded. Baseline signs and symptoms are to be recorded and followed throughout the trial. These will be monitored throughout the study and recorded if they increase in severity or frequency during treatment or within the follow up period. Participants will be assessed for adverse events by a physician or designated midlevel provider while the subject is on study. Vital signs including blood pressure, heart rate and temperature should be performed at each physical exam. Assessments may be performed more frequently if clinically indicated. In addition, hematology and serum chemistry profiles will be drawn prior to the initiation of treatment to determine whether the study drug combination affects hematologic values, electrolytes or liver function tests. Laboratory assessments will be performed more frequently if clinically indicated. This clinical and laboratory data will be used to determine whether these women in the study with Hydroxytyrosol have any symptoms or side effects associated with the study medications. Subjects will be followed for adverse events for a period of 30 days after the completion of investigational therapy. Patients with abnormal laboratory or clinical findings that are believed to be treatment related will be followed until the condition resolves or stabilizes, or until the laboratory values are no longer considered clinically significant.

CTC Version 4.0 will be used to grade toxicities. Laboratory tests may be done more frequently if medically indicated. If a participant develops any grade 3 or grade 4 toxicity possibly, probably or definitely related to the study drug, the study drug will be discontinued. If the participant develops grade 1 or 2 toxicities that are felt to be possibly, probably or definitely related to the study drug, the participant may go on a drug holiday (for no longer than 12 consecutive weeks) and restart the drug at the same dose. In each of these cases, the follow-up mammograms, breast biopsies will still be collected as per protocol one year after the initial start date of the intervention.

If CTC Grade 3 or 4 hematologic toxicity is seen, CBC + differential + platelets should be repeated weekly until recovery.

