5. Participants must have a baseline mammogram performed within 90 days prior to study entry, done on a digital mammography machine that shows either normal or benign findings. Participants with mammograms that are reported as suspicious for malignancy are eligible as long as the biopsy is negative.
6. Participants must have baseline mammographic density $> 10\%$ based upon the classification system (2 = 11-50%, "scattered fibroglandular densities"; 3 = 51-75%, "heterogeneously dense"; 4 = $>75\%$, "extremely dense"). Women with a baseline mammographic density of $\leq 10\%$ (1 = $\leq 10\%$, breasts are almost entirely fat) will not be eligible. Women with a BIRADS score of 4 will be considered eligible as long as the biopsy is benign.
7. Prior tamoxifen, raloxifene or aromatase inhibitor use is allowed provided treatment is completed at least 1 year prior to registration.
8. Participants must not have bilateral breast implants, but prior breast reduction surgery is allowed. (Breast implants are not allowed as they affect density measurements and because of the risk of rupturing the implant with biopsy).
9. Participants must have a ECOG Performance Status of 0 – 1 (see Section 11).
10. Prior anticoagulant therapy use is allowed provided therapy is discontinued at least 7 days prior to the breast biopsy in order to reduce the risk of bleeding. For subjects who have taken an anticoagulation within the past 7 days, INR (International Normalized Ratio) must be $\leq 1.5 \times$ institutional upper limit of normal and Prothrombin Time and Partial Thromboplastin Time \leq IULN prior to the breast biopsy.
11. No prior malignancy is allowed within the past five years except for the following: adequately treated skin cancer and *in situ* cervical cancer .

12. Participant must not be pregnant or nursing and must agree to use effective contraception. Hormone-based birth control (pills, patches or shots) are allowed, but switching birth control methods is discouraged while on-study as hormonal changes can affect mammographic density. Hormone replacement therapy is not allowed for post-menopausal female.
13. Individuals must not participate in any other clinical trial for the treatment or prevention of cancer unless they are no longer receiving the intervention and are in the follow-up phase only. Participants must also agree not to join such a trial while participating in this study.

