14. All participants must be informed of the investigational nature of this study and must sign and give written informed consent in accordance with institutional and federal guidelines.

Exclusion Criteria

1. No prior malignancy within the past five years except for the following: adequately treated basal cell or squamous cell skin cancer and *in situ* cervical cancer. .
2. Prior Tamoxifen or Raloxifene or aromatase inhibitor or hormone replacement therapy use in the past 1 year

6 Treatment

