6.2.2 Visits

Before the drug start, the participants will have a general physical exam including a clinical breast exam, (with consent), height, weight, medical history, abdominal circumference, blood tests (CBC, CMP, fasting lipid panel), and a bilateral mammogram (if one not available within 90 days of registration). Breast MRI images will be collected and reviewed if available. If the mammogram is read as normal or benign, participants will undergo a non-directed core needle biopsy within 30 days of signing consent. For subjects who have taken an anticoagulation within the past 7 days, INR (International Normalized Ratio) must be $\leq 1.5 \times$ institutional upper limit of normal and Prothrombin Time and Partial Thromboplastin Time \leq IULN prior to the breast biopsy. If the patient has had a bone density (within the past 1 year) than it will be collected. Participants will then receive oral hydroxytyrosol for 1 year. A six month supply of study drug will be dispensed at Day 1 and another 6 months sample on month 6 visit. Participants will complete the self-administered FACT ES score at baseline, 6 months as well as at 12 months (Form ES).

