6.2.2.8 Criteria for Removal from Protocol Treatment

- a. Evidence of any cancer at any time, including DCIS. If the pathologic review of the baseline core needle breast biopsy confirms invasive breast cancer, the participant must be removed from protocol treatment.
- b. Unacceptable toxicity (as defined in Section 8.0).
- c. A participant who becomes pregnant while on treatment will be removed from protocol treatment since hormonal changes affect mammographic density.
- d. Delay of study intervention > 12 consecutive weeks due to any reason.
- e. Completion of twelve months of study intervention.
- f. The participant may withdraw from the study at any time for any reason.
- g. All reasons for discontinuation of the intervention must be documented in the Off Treatment Notice – Prevention Studies.
8. All participants will be followed for 13 months after registration. After 13 months, no further follow-up is required.
9. Non-compliance with study drug.

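### Pregnancy and nursing are excluded only at entry while the baseline mammogram may be up to 90 days old, so a baseline film taken during or soon after nursing could produce a non-drug response in the pre-menopausal group

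*Combined protocol and SAP*

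**What the plan says.** The operative rule is section 5.1 item 12: "Participant must not be pregnant or nursing and must agree to use effective contraception". Section 4.1 summarises it: "The main exclusion criteria include women who are pregnant or breast feeding". Both describe a woman's state at entry. Neither gives a minimum time since delivery or weaning, and no other section does. Section 7.2.1 requires a pregnancy test at screening or on suspicion, which says nothing about past lactation.

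The baseline film can be older than entry. Item 5 reads "Participants must have a baseline mammogram performed within 90 days prior to study entry". Section 6.2.2 asks for "a bilateral mammogram (if one not available within 90 days of registration", so an existing film inside that window is used as it stands.

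The protocol treats hormonal state as relevant to the endpoint in three places:
- Item 12 says that "switching birth control methods is discouraged while on-study as hormonal changes can affect mammographic density".
- Section 6.2.2.8 item c says a woman who becomes pregnant on treatment "will be removed from protocol treatment since hormonal changes affect mammographic density".
- Exclusion criterion 2 bars "Prior Tamoxifen or Raloxifene or aromatase inhibitor or hormone replacement therapy use in the past 1 year". Item 7 has the same 1-year interval for the anti-oestrogens.

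Section 9 describes a single-arm study. Response is a fall in density at one year, and the pre-menopausal and post-menopausal groups of 50 are each tested against a 25% null. Covariate adjustment names age or menopausal status and is exploratory.

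**The concern.** The plan guards the density endpoint against hormonal shifts from drugs taken before entry and from pregnancy after entry. It does not guard against pregnancy or lactation shortly before the baseline film. Two kinds of woman pass the criteria as written: one imaged while nursing who weans before registration, and one imaged soon after delivery or weaning. Entry is from age 18 and mutation carriers qualify, so such women can be in the target population.

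Each woman's response is measured from one baseline film, and there is no control arm to show how much density would have moved without the drug. If that film was taken in an unusual hormonal state and density later fell back, the fall would lie within the treatment year and could not be told apart from a drug effect. The result at stake is the pre-menopausal primary proportion; the post-menopausal group is essentially unaffected.

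**Working it through.** **Inputs from section 9.** n = 50 per group, null 25%, alternative 45%, two-sided 5% level, stated power 85%, 95% binomial confidence interval for the proportion.

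**Inputs that are assumptions.** k is the number of the 50 pre-menopausal women with a baseline film affected by recent pregnancy or nursing. q is the probability that such a woman meets the response cut-off when the drug does nothing. The documents give neither.

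**Step 1: the plan's own figure.** With the arcsine approximation, power = Φ(2[arcsin√0.45 − arcsin√0.25]·√50 − 1.96) = Φ(2 × [0.7353 − 0.5236] × 7.071 − 1.96) = Φ(2.994 − 1.96) = 84.9%. The normal approximation with continuity correction gives 84.0%. The stated 85% reproduces and is not in dispute.

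**Step 2: the count that would be read as success.** The exact (Clopper-Pearson) 95% lower limit is 24.7% at 19/50 and 26.4% at 20/50. The interval first lies above 25% at 20 responders. With a true rate of 25%, P(X ≥ 20) = 1.4%, against a nominal upper tail of 2.5%.

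**Step 3: add k affected women, no drug effect.**
- Expected proportion = [(50 − k) × 0.25 + k × q] / 50. With q = 1 each woman adds 0.75/50 = 1.5 points, so k = 2 gives 28.0%, k = 3 gives 29.5% and k = 5 gives 32.5%.
- P(X ≥ 20) = Σⱼ P(Bin(k, q) = j) × P(Bin(50 − k, 0.25) ≥ 20 − j), summed over j = 0 to k.

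| k | q = 0.5 | q = 0.6 | q = 1 |
|---|---|---|---|
| 0 | 1.4% | 1.4% | 1.4% |
| 1 | 1.7% | 1.8% | 2.3% |
| 2 | 2.1% | 2.4% | 3.7% |
| 3 | 2.5% | 3.0% | 5.9% |
| 5 | 3.6% | 4.9% | 13.3% |

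**Step 4: reading the table.** One affected woman leaves the error below 2.5% even if she is certain to respond. Two take it past 2.5% if both are certain to respond, but not at 60%. Three take it past at 60% and only just reach it at 50%.

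**Step 5: what q depends on.** Section 9 gives two response definitions in one paragraph: a 10% absolute reduction, and a reduction of at least 25% from baseline. They must be reconciled before anyone can say how large a non-drug fall would have to be to count.

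**The case against.** A reader might infer that density does fall after weaning and that such a woman will be scored as a hydroxytyrosol responder. The documents do not support that. They say that hormonal changes affect density. They do not say that lactation raises it, that weaning lowers it, that the change falls within the treatment year, or that it reaches either cut-off in section 9. This part of the objection stands in full, so the effect is conditional.

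The number of such women may also be very small. A woman imaged while nursing would have to wean within the 90 days or less between film and registration. Women imaged soon after delivery or weaning are a wider route, but their frequency is equally unknown. Because the exact test starts at 1.4%, it can absorb one such woman. This stands too and limits the priority.

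Nor is pregnancy uncontrolled in general. Contraception is required, a serum pregnancy test is done at screening, pregnancy on treatment leads to removal, a medical history is taken at baseline, and the date of last menses is reviewed at follow-up. These are real controls, but none covers the period before the baseline film. The gap is in the look-back only.

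Finally, the 1-year interval was set for drugs and hormone replacement. Nothing in the documents shows that it suits delivery or weaning, and item 12 tolerates some hormonal variation by allowing hormonal contraception. So the length of any interval needs its own justification.

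**Conclusion.** The point holds as a narrow eligibility gap with a conditional consequence. As written, the criteria admit a woman whose baseline film was taken during nursing or soon after delivery or weaning, and the plan has no control arm or sensitivity analysis that would reveal the effect on her result.

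The bias towards a false positive rests on three assumptions: that density falls back after delivery or weaning, that the fall meets the cut-off finally adopted, and that more than one such woman enrols. If they hold, two or three women are enough to move the pre-menopausal upper-tail error above 2.5%, with the size depending on how likely each is to respond. If any fails, the effect is negligible. The sample size and the stated power are not affected. Priority is low to moderate: the effect is uncertain and the remedy is cheap.

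**What to change.** 1. In section 5.1 item 12, and in the section 4.1 summary, apply the pregnancy and nursing exclusion at the date of the baseline mammogram and for a stated interval before it. The sponsor should justify the length; the 1-year hormonal look-back already in the protocol is one candidate.
2. Record the date of last delivery or weaning for every pre-menopausal woman, including those already enrolled. This also shows how many women are affected.
3. In section 9, pre-specify a sensitivity analysis that repeats the pre-menopausal primary proportion and its 95% interval without women inside the interval.
4. Reconcile the two response definitions in section 9, so that it is clear what size of fall counts.

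The cost is one eligibility line, one history question and one extra analysis. The planned sample size and stated power do not change. The downside is that a few pre-menopausal women would be deferred or excluded, and the sensitivity analysis would rest on slightly fewer than 50.
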